Eligible participants will be instructed to maintain stable dietary and exercise habits and for the duration of the study, to avoid vigorous physical activity for 24hr before each visit and to and consume their normal dinner the night before each visit. At each visit current use of medications and natural health products participants will be reviewed with each participant and any changes will be discussed with the investigator. Female participants will be advised that if they become pregnant during the study they are to contact the investigators and discontinue their participation immediately.

Each subject will be studied on 6 separate days with at least a 3-day interval between tests. On each test day, subjects will come to GI Labs ([name]) in the morning after a 10-14h overnight fast. On each test occasion the subject will be weighed, and give fasting finger-prick and venous blood samples. Blood from a forearm vein will be collected into a 6ml EDTA tube (Vacutainer, BD Canada, Mississauga, ON). Finger-prick blood samples will be collected into 2 separate vials: one (2-3 drops blood into a fluoro-oxalate tube) for glucose analysis and the other (6-8 drops of blood into an 0.3ml Microvette with clot activator, Sarsted, Germany) for insulin. After the fasting sample the subject will take 12 capsules or 2 tablets with a drink of 250ml water. Subjects will rest for 3-10min and have their blood pressure measured; 40min after swallowing the first capsule or tablet a finger-prick blood sample (2-3 drops for glucose and 6-8 drops for insulin analysis) will be collected and then subjects will consume 82.5g dextrose (containing 75g anhydrous glucose) dissolved in 300ml water within 5min plus a drink of 150ml water within 10min of starting the glucose drink. Further finger-prick blood samples for glucose (2-3 drops) and insulin (6-8 drops) will be obtained at 15, 30, 45, 60, 90 and 120 min after starting to drink the glucose solution. Venous blood samples (7ml) will be collected after the 60 and 120 min finger-prick. During the test subjects will remain seated quietly except for trips to the washroom if necessary. After the last blood sample subjects will be offered a snack and be free to leave.

Treatments

The 6 treatments administered will consist of the following:

- 12 placebo capsules with 250ml water (0g Axulin)
- 250ml water alone (0g Axulin)

- 4 placebo and 8 Axulin capsules (2g Axulin)
- 16 Axulin capsules (4g Axulin)

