The GI Testing protocol has been approved by the Western Institutional Review Board® which meets all requirements of the US Food and Drug Administration (FDA), the Department of Health and Human Services (DHHS), the Canadian Health Protection Branch (HPB), Canadian

Institutes for Health Research (CIHR) and the European Community Guidelines. Informed consent is obtained from all subjects for each series of tests they participate in.

Participant Withdrawal Criteria

The Investigator may elect to withdraw the participant from the study or the participant may withdraw from the study at any time. Reasons for withdrawing include, but are not limited to:

- Development of an exclusion criterion during the course of the study
- Study product never consumed
- Participant was lost to follow-up
- Participant did not follow study procedures
- Participant elected to withdraw from the study for any reason
- Investigator elected to remove participant from the study for any reason
- Subject takes longer than the specified time to complete the study

In the case of premature withdrawal, all planned assessments for the end of the study visit will be completed and the sponsor will be informed as soon as possible. The subject's Case Report Form ("CRF") will be completed including the final assessment. The date and main reason for the premature withdrawal will be clearly documented in the subject's file and written down on the CRF

ADVERSE EVENT REPORTING

An adverse event (AE) is any symptom, injury, illness, or medical/surgical procedure whether planned or not or whether associated with the study foods or not. AEs will be assessed at each visit and recorded in the Case Report Forms. AEs will be evaluated for duration, severity, seriousness, and causal relationship to the food items provided in the study by the study physician who will decide if any action is required and provide referral, treatment, and/or follow-up as appropriate until resolved, judged to no longer be clinically significant, or if a chronic condition, until fully characterized. Research staff will record the final outcome and resolution date of the event wherever possible. The action taken and the outcome will be recorded in the Case Report Form.

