It is anticipated that participants enrolled in the study will be clinically managed without the need to add medications or to change the dosage(s) assigned to their current medications. In the event that additional medication is required, or an increase in their medication dosage is warranted, these changes will be recorded as adverse events.

Investigators are required to report adverse events that fit the following criteria within 10 working days of the time the investigator becomes aware of them:

- Event is **Unexpected** (in terms of nature, severity, or frequency) given (a) the research procedures that are described in the protocol-related documents, such as the IRB-approved research protocol and informed consent document, or the

Investigator Brochure; and (b) the characteristics of the subject population being studied.

- **Related or possibly related** to participation in the research (possibly related means there is a reasonable possibility that the incident, experience, or outcome may have been caused by the procedures involved in the research); and
- Suggests that the research **places subjects or others at a greater risk of harm** (including physical, psychological, economic, or social harm) than was previously known or recognized.

If the adverse event is clearly not related to the study drug, device, procedures, or washout process, it would not represent a risk to other subjects in the research or a “problem” for the study and, therefore, does not have to be reported to WIRB.

The Principal Investigator, [name], will be informed within 48 hrs of the nature of the reportable AE and the treatment allocation of the participant in whom it occurred by sending a copy of the AE report via email ([contact]). [name] will track all reportable AEs and notify the sponsors if they occur.

In addition to the above, all adverse events will be reported to Health Canada. All serious adverse events (any adverse event that results in death, is life-threatening, requires in-patient hospitalization or prolongation of existing hospitalization, results in persistent or significant disability/incapacity or is a congenital anomaly/birth defect) will be reported to Health Canada, the Sponsor and the IRB within 24hr of their ascertainment.

Risks

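### No adverse-event contact is described after the last dose, although each of a completer's first five treatments is followed by an adverse-event check at least 3 days later

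*Combined protocol and SAP*

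**What the plan says.** Under ADVERSE EVENT REPORTING, the scheduled collection of AEs is tied to the visits: "AEs will be assessed at each visit and recorded in the Case Report Forms". The same section has the study physician follow events to resolution or full characterisation, and it states a broad reporting duty: "In addition to the above, all adverse events will be reported to Health Canada".

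PROCEDURES sets the calendar: "Each subject will be studied on 6 separate days with at least a 3-day interval between tests". The Blinding section provides one treatment bag per visit for all six visits, so visit 6 is a dosing day like the others. Within a visit, the pre-glucose sample is taken "40min after swallowing the first capsule or tablet a finger-prick blood sample" and the last sample comes 120 min after the start of the glucose drink. Then: "After the last blood sample subjects will be offered a snack and be free to leave".

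A closing assessment is mentioned only under Participant Withdrawal Criteria. After premature withdrawal, "all planned assessments for the end of the study visit will be completed and the sponsor will be informed as soon as possible", and the case report form "will be completed including the final assessment". Neither the content nor the timing of these assessments is given, and PROCEDURES schedules no visit beyond the six test days.

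**The concern.** Collecting AEs at visits works for a dose that has a visit after it. A rash or loose stools starting at home after treatments 1 to 5 can be asked about at the next test day. The last treatment has no next test day. An AE question may well be asked during visit 6, since its timing within a visit is not specified, but it could cover only the hours on site. On the text as written, an event starting after the participant leaves would come to light only if the participant reported it unprompted.

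Three features of the protocol argue against assuming that every effect appears early:

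- The Risks section lists severe gastrointestinal symptoms, eczema and rashes as rare forms of intolerance, and nothing confines them to the time on site.
- The Treatments section gives possible slower bioavailability as its reason for testing tablets, and half of the orders in Table 1 end in the tablet and water block.
- The reassurance under Risks is argued from resistant maltodextrins and resistant starch, which are not among the six treatments, so it says little about Axulin either way.

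What is at stake is the completeness of the AE record for one of each participant's six treatments. The glucose endpoint is not touched.

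**Working it through.** The plan states no length for AE observation, so there is no figure of its own to reproduce. The check covers the observation time after each treatment and the number of Axulin doses affected.

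**Observation time**

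- First capsule or tablet to glucose drink: 40 min (PROCEDURES).
- Start of glucose drink to last sample: 120 min (PROCEDURES).
- Total at visit 6: 40 + 120 = 160 min, plus an untimed snack.
- Treatments 1 to 5, completers: next visit at least 3 days later, 3 × 24 × 60 = 4,320 min. 4,320 / 160 = 27, so the minimum interval is 27 times as long.

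**Provisions that might fill the gap**

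- Physician follow-up applies to events already identified; it does not find new ones.
- The 24-hour reporting of serious events runs from ascertainment, so someone must first learn of the event.
- The closing assessments in the withdrawal text are tied to a visit, and the only visits scheduled after screening are the six test days.
- The only participant-initiated contact described in PROCEDURES concerns pregnancy.

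**Axulin doses given at visit 6**

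Visit 6 codes over the 24 orders in Table 1:

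| Code | A | B | C | D | E | F |
|---|---|---|---|---|---|---|
| Orders ending on it | 4 | 4 | 4 | 6 | 2 | 4 |

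One of A–C is placebo and one of D–F is the empty bag (water alone). Which ones is in the sealed envelope, so a range is needed.

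- Capsule block: 12 orders end here. Whichever code is placebo, 12 − 4 = 8 end on Axulin.
- Tablet block: 12 orders end here. Removing the water code leaves 12 − 6 = 6, 12 − 2 = 10 or 12 − 4 = 8.
- Total: 8 + 6 = 14 to 8 + 10 = 18 of 24 orders.
- Each order contains four Axulin doses, so 24 × 4 = 96 in all. 14/96 = 14.6% and 18/96 = 18.8%.
- Axulin doses with a later visit: 96 − 18 = 78 to 96 − 14 = 82, or 81.3–85.4%.

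**Sensitivity to 22 rather than 24 orders**

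The protocol recruits 22. Assume IDs 12 and 32 go unused; they end on C and B. The visit 6 counts become A4 B3 C3 D6 E2 F4. The capsule block gives 10 − 4 = 6 or 10 − 3 = 7, and the tablet block still gives 6 to 10. The total is 12 to 17 of 22 × 4 = 88 doses, or 13.6–19.3%. The percentage barely changes.

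**The case against.** The strongest reply is that the gap exists but matters little. No objective concerns safety. Doses are single, taken on site, and made from extracts of foods in normal diets. The Risks section expects no gastrointestinal symptoms, or very mild ones.

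The crossover also softens the gap. A completer who ends on Axulin has already had three Axulin doses, each with a later visit. Because capsules and tablets are given in separate blocks, one of those three was the same gram dose in the other form. Intolerance that recurs on re-exposure would probably have shown before visit 6. This stands and is a good reason to rate the point low, but it does not cover a first event after the last dose.

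Three further points carry some weight:

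- The consent pages and the case report form are not available and may tell participants to report later symptoms. The finding is therefore limited to the protocol text. Such an instruction would still rely on participants volunteering events.
- The Health Canada sentence applies to events once known. It promises no active surveillance after participants leave, so the protocol does not contradict itself. The sentence only shows that a full AE record is wanted.
- Three days is the interval between tests, not a stated AE window. It is used here only to give the last dose the same minimum follow-up as the others; the documents do not establish it as the right window for this product.

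**Conclusion.** The concern holds as a minor one, at the level of something to consider. Followed exactly, the plan leaves the last treatment without the later AE check that every earlier treatment gets. It affects one of each participant's six treatments, and 14 to 18 of the 96 Axulin doses in Table 1 (15–19%).

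The count assumes that all 24 orders are used and completed. For a participant who withdraws early, the last treatment taken may also lack a later visit. No number of missed events can be given, because the documents report no rate of delayed events, and the expected burden is low.

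**What to change.** Add one or two sentences scheduling a telephone or e-mail contact at least 3 days after visit 6. It should ask the same AE question as at the visits and record any event against the last treatment taken. For withdrawals, keep the prompt final assessment and sponsor notification as they are, and add the same contact at least 3 days after the last dose where the participant can be reached.

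The cost is about 22 brief contacts by existing staff. The 10–15 min per contact is an assumption; the rate, hours and total are from BUDGET.

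- Time: 22 × 10 min = 3.7 h to 22 × 15 min = 5.5 h, or 2.5–3.8% of the 144 coordinator hours.
- Money: at $45 per hour, $165 to $247.50 CDN, or 0.16–0.23% of $105,500.
- Follow-up closes a few days later for each participant.

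The Informed Consent section says "The GI Testing protocol has been approved by the Western Institutional Review Board", so a minor amendment may be needed. Its cost is not given. The only related figure is the $4,375 budgeted for the WIRB submission, so an amendment fee, if charged, could exceed the staff cost. Treatments, blinding, blood sampling and the glucose analysis stay as they are.

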The primary endpoint is the % reduction in 2-hour incremental AUC for glucose. Using the t-distribution with 2-tailed $p<0.05$ and assuming an average CV of within-individual variation of 2-hour incremental AUC values of 25%, $n=20$ subjects (10 lean and 10 overweight) has 80% power to detect a 17% difference in AUC, 90% power to detect a difference of 19% and 99% power to detect a difference of 26%. Within each subject group ($n=10$) there is 80% power to detect a difference in AUC of 25%, and 80% power to detect a 33% difference between the responses of lean and overweight subjects. To allow for 10% dropout, we will recruit $n=11$ lean and $n=11$ overweight subjects.

Subject Recruitment

Participants will be recruited from the pool of participants at GI Laboratories who have indicated that they are willing to be contacted and asked if they wish to participate in new studies. If an insufficient number of subjects can be recruited, then a newspaper advertisement will be used to recruit new subjects.

Selection of participants

Participants willing to be considered will be invited to come to the research centre to have the study procedures explained to them and be given a copy of the consent form which they may either sign then, take away to sign at a later date, or decline to participate. Participants will be encouraged to ask any questions they may have and not to sign the consent form until all of their questions have been answered to their satisfaction. Those who consent to participate will come to the research centre for a pre-selection visit when subject eligibility will be determined. During this visit, the 10-14hr overnight fasted participants will complete a questionnaire (Appendix 1) to assess medical history, and lifestyle factors, have height, weight, waist circumference and blood pressure measured, and have a blood sample drawn for measurement of glucose, HbA1c, lipids, creatinine, AST, ALT and complete blood count. Females will have a pregnancy test.

PROCEDURES

The study will have a randomized block design with repeated measures. One block, which will be double-blinded, will test the effect of Axulin capsules; the other block, which will be open label, will test the effect of Axulin tablets. Within each participant, the order of the blocks will be randomized and within each block the order of the treatments will be randomized.

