- 2 Axulin tablets (2g Axulin)
- 4 Axulin tablets (4g Axulin)

Each placebo capsule contains 250mg inulin, each identical-looking Axulin capsule contains 250mg Axulin. It is anticipated that Axulin will be sold in tablets because 1g can be compacted into a tablet without loss of biological activity, but, because Axulin is a low-density powder, only 400mg can be placed in a capsule of similar size. We will use capsules in this study because it is more economical to produce the relatively small number of identical-looking placebo capsules required as compared to producing placebo tablets. To obtain doses in 1g increments, we will use smaller capsules containing 250mg each. The rationale for including tablets in the study is that Axulin in tablet form might be more slowly bioavailable than when encapsulated; thus, it is

important to determine whether the effects of Axulin tablets on postprandial responses is similar to the same dose taken in capsules.

Blinding

The number of Placebo and Active Axulin capsules and tablets required for the study will be provided to GI Labs. A person not involved in any other aspect of the study will make up 6 small zip-lock plastic bags for each subject labelled with a subject number and visit number and containing the treatment for visits 1 through 6 (the bag for the water alone treatment will be empty). The treatments will be randomized as shown in Table 1. The order of the blocks and the order of the treatments within each block were randomized using the @rand() function of Excel with 2 blocks of 6 created for lean subjects and 2 blocks for overweight subjects; the 2 extra orders are for use in case of drop-outs so that at least n=20 subjects complete the study (see Table 1). The person labeling and filling the bags with the treatments will assign the treatments to the codes and place the treatment assignments in a sealed opaque envelope kept in an accessible location. The envelope will be opened only after the study has been completed and the database locked, or in case of emergency if required for participant safety.

Table 1: Randomization Scheme

ID	Group	Visit 1	Visit 2	Visit 3	Visit 4	Visit 5	Visit 6
1	Lean	A	B	C	E	D	F
2	Lean	B	C	A	E	F	D
3	Lean	F	D	E	C	A	B
4	Lean	B	A	C	F	E	D
5	Lean	D	E	F	A	C	B
6	Lean	D	F	E	C	B	A
7	Lean	F	D	E	A	C	B
8	Lean	C	B	A	D	E	F
9	Lean	D	F	E	B	C	A
10	Lean	C	A	B	E	D	F
11	Lean	B	A	C	E	F	D
12	Lean	F	E	D	A	B	C
21	Overweight	D	E	F	C	B	A
22	Overweight	F	D	E	B	A	C
23	Overweight	A	B	C	E	D	F

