24	Overweight	A	C	B	F	E	D
25	Overweight	B	C	A	E	F	D
26	Overweight	C	A	B	D	F	E

27	Overweight	B	C	A	F	D	E
28	Overweight	D	F	E	B	A	C
29	Overweight	D	E	F	C	B	A
30	Overweight	F	E	D	A	B	C
31	Overweight	A	C	B	E	F	D
32	Overweight	E	D	F	C	A	B

Instructions: please assign capsules to codes A, B or C, and tablets or empty bag to codes D, E or F. Place treatment assignments into a sealed opaque envelope and keep the envelope in an accessible location. Treatments are as follows:

BLOCK 1 (A, B or C)

- Placebo 1; 16 Placebo capsules
- 2g Axulin caps: 4 Placebo capsules plus 8 Axulin capsules
- 4g Axulin caps: 16 Axulin capsules

BLOCK 2 (D, E or F)

- empty bag
- 2g Axulin tablets: 2 Axulin tablets
- 4g Axulin tablets: 4 Axulin tablets

Biochemical Analysis

Finger-prick blood samples for glucose analysis will be placed in the refrigerator immediately after being obtained and at the end of the test placed in a -20°C freezer until analysis which will be performed within 5 days. Glucose analysis is done using an YSI model 2300 STAT analyzer (Yellow Springs, OH). The microvette tubes used to collect blood for insulin analysis will be centrifuged at 3622×g for 2 min and the serum transferred to labeled polypropylene tubes and stored at -20°C prior to analysis of insulin using the Human Insulin EIA Kit (Alpco Diagnostics). Venous blood samples will be stored at 4°C until the end of the study after which they will be centrifuged at ~1400×g for 10 min and the plasma removed and separated into 2×1ml aliquots; 1 for analysis of triglycerides at St. Michael's Hospital biochemistry laboratory and the other for measurement of the active ingredient in Axulin by liquid chromatography/mass spectrometry.

Statistical Analysis

Incremental areas under the blood glucose, insulin and triglyceride response curves (AUC), ignoring area below fasting, will be calculated. Blood glucose and insulin concentrations and AUC values will be analyzed using repeated measures ANOVA examining for the main effects of dose, form (tablets vs capsules) and subject group (lean vs overweight) and their interactions. After demonstration of significant heterogeneity, differences between individual means will be assessed using Tukey's test to adjust for multiple comparisons.

Informed Consent

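### The adverse event rule discloses treatment allocation where the blinding rule forbids it, and one capsule key shared by all participants carries each disclosure beyond the person affected

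*Combined protocol and SAP*

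**What the plan says.** The Procedures section divides the study into two blocks. "One block, which will be double-blinded, will test the effect of Axulin capsules". The second block, with the tablets and the empty bag, is not blinded. The capsule block is therefore the only blinded part.

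The Blinding section has one uninvolved person fill the bags, match treatments to code letters and seal the result in an envelope. "The envelope will be opened only after the study has been completed and the database locked", with one exception: an emergency in which a participant's safety calls for it. The instructions under Table 1 tell that person: "please assign capsules to codes A, B or C, and tablets or empty bag to codes D, E or F". This is a single assignment for the whole table. Table 1 then prints the code letter for every participant at every visit.

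Adverse Event Reporting sets a different rule. For each reportable event the Principal Investigator "will be informed within 48 hrs of the nature of the reportable AE and the treatment allocation of the participant in whom it occurred", and this is done "by sending a copy of the AE report via email". An event is reportable when it meets three conditions together: it is unexpected, it is at least possibly related to the research, and it points to a greater risk than was known. None of the three is the emergency test in the Blinding section, and neither section refers to the other.

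**The concern.** A possibly related and unexpected reaction can meet all three reporting conditions without being an emergency. For such an event, staff cannot both keep the envelope sealed and send the allocation. The envelope is the only allocation record the protocol describes, and no separate unblinded reporting route is given.

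The shared key makes the conflict more serious. Once the meaning of a letter is known for one participant, Table 1 shows where that letter falls for all the others. Even an opening that the Blinding section permits would expose the key for everyone.

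What is at stake is the set of judgements made while the study runs. The withdrawal criteria include "Investigator elected to remove participant from the study for any reason" and failure to follow study procedures. The study physician judges the causality of adverse events. Spare randomization orders are held so that at least 20 participants complete, and with 20 completers one discretionary removal changes 1/20 = 5% of the sample. In a double-blind block these decisions should be made without knowledge of treatment.

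**Working it through.** The plan states no figure on this point, so there is nothing to reproduce. The check counts how many capsule keys remain possible after one report.

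**Inputs**
- Three capsule treatments (placebo, 2 g, 4 g) on codes A, B and C, with one key for all: Blinding section and Table 1 instructions.
- 24 sequences, each containing every code once: Table 1. This gives 24 × 3 = 72 capsule visits, 24 per code.
- 22 participants to be recruited: Number of subjects. This gives 22 × 3 = 66 capsule visits, 22 per code. For 20 completers the total is 20 × 3 = 60.
- Capsules per visit, in the order placebo / 2 g / 4 g: 16/12/16 in the Table 1 instructions and 12/12/16 in the Treatments list. The two places disagree, so both are carried through.

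**Step 1: before any report.** There are 3! = 6 possible keys. For someone who can see the number of capsules, either set of counts singles out one treatment (2 g under 16/12/16, 4 g under 12/12/16). That leaves 2! = 2 keys, with 22 visits already identifiable.

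**Step 2: after one report.** Each cell gives the keys remaining and the capsule visits decoded, for 22 participants.

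| Content of the report | Counts not used | Counts 16/12/16 | Counts 12/12/16 |
|---|---|---|---|
| Participant's whole sequence | 1 key, 66 visits | 1 key, 66 visits | 1 key, 66 visits |
| Event visit only: placebo capsules | 2 keys, 22 visits | 1 key, 66 visits | 1 key, 66 visits |
| Event visit only: 2 g capsules | 2 keys, 22 visits | 2 keys, 22 visits (nothing added) | 1 key, 66 visits |
| Event visit only: 4 g capsules | 2 keys, 22 visits | 1 key, 66 visits | 2 keys, 22 visits (nothing added) |
| Event visit only: open-label block | 6 keys, 0 visits | 2 keys, 22 visits (from counts alone) | 2 keys, 22 visits (from counts alone) |

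**Step 3: reading the table.** Disclosure of the whole sequence always breaks the capsule block. Disclosure of one capsule visit breaks one code for everyone. With the counts, it completes the key if the treatment is one of the two with equal counts, and adds nothing if the count had already identified it. An event-visit report from the open-label block never decodes A, B or C.

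**Step 4: with a separate key for each participant.** A disclosure could reach at most that participant's 3 capsule visits, not 66.

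**The case against.** The strongest reply has five parts.

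- *The conflict may be only apparent.* The Blinding section governs the envelope, and the adverse event section never mentions it. The allocation to be reported could mean the Table 1 code letter, and some reportable events will also be emergencies. This stands only in part. The product is the more natural meaning, nothing limits the rule to emergencies, and the text does not settle the question.
- *The trigger is narrow.* Three conditions must hold together, in healthy adults taking supervised single doses, and the Risks section expects no gastrointestinal symptoms or very mild ones. This stands: no reportable event at all is plausible.
- *One report need not unblind the block.* A reader might infer that any single report does so. The documents do not support that. It follows only from a whole-sequence report, or from an event-visit report on one of the two equal-count treatments read together with the counts. A reader might equally infer that the block starts with 66 fully blinded visits, and that an event-visit report leaves 44 at even odds. That holds only if the capsule counts are ignored.
- *The affected roles are not stated.* The protocol does not say whom the double-blind covers, describes no onward disclosure to visit staff, and does not say that the Principal Investigator and the study physician are the same person. This stands as a limit on the harm pathway.
- *Bias in the result is not shown.* Glucose is measured by an analyser, every participant receives every treatment, and the same judgements are already made unblinded in the open-label block. This stands. A reader might infer that the glucose result would be biased, but nothing in the documents establishes or sizes such a bias.

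**Conclusion.** The point holds as an unreconciled conflict between two stated rules, made worse by a key common to all participants. Confidence is high for the conflict and conditional for its reach.

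For 22 participants, a whole-sequence report exposes 66 capsule visits. An event-visit report on a capsule treatment exposes 22 if counts are ignored. With the printed counts it exposes all 66, or no more than the 22 already identifiable. These are ceilings, because they include visits already completed when the report is sent.

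The conclusion rests on two assumptions: that the allocation to be reported means the product received, and that the double-blind is meant to include the Principal Investigator. Both are reasonable readings, but neither is stated. The likely consequence is exposure of withdrawal, protocol-deviation and causality decisions, not error in the assay. The plan should be changed because the correction is cheap and protects its only double-blind block.

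**What to change.** 1. Reconcile the Blinding and Adverse Event Reporting sections. For capsule visits, have the 48-hour report give participant ID, visit number and code letter. Reveal the allocation only under the emergency exception already in the Blinding section, and only for that participant and visit.
2. Assign treatments to codes A, B and C separately for each participant. Alternatively, replace the single envelope with sealed envelopes per participant and visit for the capsule block only: 22 × 3 = 66, or 24 × 3 = 72 if the spare orders are covered. Open-label visits need none.
3. State which roles are blinded in the capsule block.
4. Separately, reconcile the capsule counts in the Treatments list and the Table 1 instructions. As printed they disagree, and either set separates one capsule treatment by number alone.

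The cost is a short wording change in the adverse event section, a line on roles, and either a per-participant key or 66 to 72 small envelopes. The person who already fills the bags by subject and visit can prepare them. No participants, visits or staff are added, and safety reporting and emergency unblinding remain available.
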